#### 11.1.4 Response Criteria

##### 11.1.4.1 Evaluation of Target Lesions

Complete Response (CR): Disappearance of all target lesions. Any pathological lymph nodes (whether target or non-target) must have reduction in short axis to <10 mm (<1 cm).

Partial Response (PR): At least a 30% decrease in the sum of the diameters of target lesions, taking as reference the baseline sum diameters.

Progressive Disease (PD): At least a 20% increase in the sum of the diameters of target lesions, taking as reference the smallest sum on study (this includes the baseline sum if that is the smallest on study). In addition to the relative increase of 20%, the sum must also demonstrate an absolute increase of at least 5 mm (0.5 cm). (Note: the appearance of one or more new lesions is also considered progressions).

Stable Disease (SD): Neither sufficient shrinkage to qualify for PR nor sufficient increase to qualify for PD, taking as reference the smallest sum diameters while on study.

##### 11.1.4.2 Evaluation of Non-Target Lesions

Complete Response (CR): Disappearance of all non-target lesions and normalization of tumor marker level. All lymph nodes must be non-pathological in size (<10 mm [ $<1$  cm] short axis).

Note: If tumor markers are initially above the upper normal limit, they must normalize for a patient to be considered in complete clinical response.

Non-CR/Non-PD: Persistence of one or more non-target lesion(s) and/or maintenance of tumor marker level above the normal limits.

Progressive Disease (PD): Appearance of one or more new lesions and/or *unequivocal progression* of existing non-target lesions. *Unequivocal progression* should not normally trump target lesion status. It must be representative of overall disease status change, not a single lesion increase.

Although a clear progression of “non-target” lesions only is exceptional, the opinion of the treating physician should prevail in such circumstances, and the progression status should be confirmed at a later time by the review panel (or Principal

Investigator).

#### 11.1.4.3 Evaluation of 18F-FDG PET CT Target:

**Complete Response (CR):** A metabolic complete response on PET/CT will be defined as greater than -66% reduction in tumor FDG uptake at sites of abnormal tumor FDG uptake noted on pre-treatment FDG-PET study (considering normal cardiac or liver blood pool).

**Partial Response (PR):** A metabolic partial response on PET/CT will be defined as -25% to -66% reduction in tumor FDG uptake at sites of abnormal tumor FDG uptake noted on pre-treatment FDG-PET study (considering normal cardiac or liver blood pool).

**Progressive Disease (PD):** Progressive metabolic disease on PET/CT is classified as an increase in tumor FDG uptake greater than +25% within the tumor region defined on baseline scan (considering normal cardiac or liver blood pool), or appearance of new FDG uptake in new metastatic lesions.

**Stable Disease (SD):** Stable metabolic response will be defined as a change in tumor FDG uptake by less than +25% (increase) or by less than -25% (decrease) at sites of abnormal tumor FDG uptake (considering normal cardiac or liver blood pool) when compared to pre-treatment FDG-PET study.

Patients with a global deterioration of health status requiring discontinuation of treatment or die without objective evidence of disease progression at that time should be reported to be off study treatment due to "symptomatic deterioration." Every effort should be made to document the objective progression even after discontinuation of treatment.

##### 11.1.4.3.1 Duration of Response

Duration of overall response: The duration of overall response is measured from the time measurement criteria are met for CR or PR (whichever is first recorded) until the first date that recurrent or progressive disease is objectively documented (taking as reference for progressive disease the smallest measurements recorded since the treatment started). The duration of overall CR is measured from the time measurement criteria are first met for CR until the first date that progressive disease is objectively documented.

Duration of stable disease: Stable disease is measured from the start of the treatment until the criteria for progression are met, taking as reference the smallest measurements recorded since the treatment started, including the baseline measurements.

#### 11.1.4.4 Evaluation of Overall Response

The overall response is the response recorded from the start of the treatment until the 3-month post-treatment PET-CT.

**For Patients with Measurable Disease (i.e., Target Disease)**

Target Lesions	Non-Target Lesions	New Lesions*	Overall Response
CR	CR	No	CR
CR	Non-CR/Non-PD	No	PR
CR	Not evaluated	No	PR
PR	Non-CR/Non-PD/not evaluated	No	PR
SD	Non-CR/Non-PD/not evaluated	No	SD
PD	Any	Yes or No	PD
Any	PD**	Yes or No	PD
Any	Any	Yes	PD

\*See RECIST 1.1 manuscript for further details on what is evidence of a new lesion.  
 \*\*In exceptional circumstances, unequivocal progression in non-target lesions may be accepted as disease progression.  
Note: Patients with a global deterioration of health status requiring discontinuation of treatment without objective evidence of disease progression at that time should be reported as “*symptomatic deterioration*.” Every effort should be made to document the objective progression even after discontinuation of treatment.

**For Patients with Non-Measurable Disease (i.e., Non-Target Disease)**

Non-Target Lesions	New Lesions	Overall Response
CR	No	CR
Non-CR/non-PD	No	Non-CR/non-PD*
Not all evaluated	No	not evaluated
Unequivocal PD	Yes or No	PD
Any	Yes	PD

\* ‘Non-CR/non-PD’ is preferred over ‘stable disease’ for non-target disease since SD is increasingly used as an endpoint for assessment of efficacy in some trials so to assign this category when no lesions can be measured is not advised

## **12. DATA REPORTING / REGULATORY REQUIREMENTS**

Adverse event lists, guidelines, and instructions for AE reporting can be found in Section 7.0 (Adverse Events: List and Reporting Requirements).

### **12.1 Study Oversight**

This protocol is monitored at several levels, as described in this section. The Protocol Principal Investigator is responsible for monitoring the conduct and progress of the clinical trial, including the ongoing review of accrual, patient-specific clinical and laboratory data, and routine and serious adverse events; reporting of expedited adverse events; and accumulation of reported adverse events from other trials testing the same drug(s). The Protocol Principal Investigator and statistician have access to the data at all times through the CTMS web-based reporting portal.

For the Phase 1 portion of this study, all decisions regarding dose escalation/expansion/de-escalation require sign-off by the Protocol Principal Investigator through the CTMS/IWRS. In addition, for the Phase 1 portion, the Protocol Principal Investigator will have at least monthly, or more frequently, conference calls with the Study Investigators and the CTEP Medical Officer(s) to review accrual, progress, and adverse events and unanticipated problems.

All Study Investigators at participating sites who register/enroll patients on a given protocol are responsible for timely submission of data via Medidata Rave and timely reporting of adverse events for that particular study. This includes timely review of data collected on the electronic CRFs submitted via Medidata Rave.

All studies are also reviewed in accordance with the enrolling institution's data safety monitoring plan.

### **12.2 Data Reporting**

Medidata Rave is a clinical data management system being used for data collection for this trial/study. Access to the trial in Rave is controlled through the CTEP-IAM system and role assignments.

Requirements to access Rave via iMedidata:

- A valid account, and
- Assigned a Rave role on the LPO or PO roster at the enrolling site of: Rave CRA, Rave Read Only, Rave CRA (LabAdmin), Rave SLA, or Rave Investigator.

Rave role requirements:

- Rave CRA or Rave CRA (Lab Admin) role, must have a minimum of an Associate Plus (AP) registration type,
- Rave Investigator role, must be registered as an Non-Physician Investigator (NPIVR) or Investigator (IVR), and

NCI Protocol #: 9892

Version Date: January 12, 2023

- Rave Read Only role, site staff must have at a minimum an Associates (A) registration type.
- Refer to <https://ctep.cancer.gov/investigatorResources/default.htm> for registration types and documentation required.

Upon initial site registration approval for the study in Regulatory Support System (RSS), all persons with Rave roles assigned on the appropriate roster will be sent a study invitation email from iMedidata. To accept the invitation, site staff must either click on the link in the email or log in to iMedidata via the CTSU members' website under *Data Management > Rave Home* and click to accept the invitation in the Tasks pane located in the upper right-corner of the iMedidata screen. Site staff will not be able to access the study in Rave until all required Medidata and study specific trainings are completed. Trainings will be in the form of electronic learnings (eLearnings) and can be accessed by clicking on the eLearning link in the *Tasks* pane located in the upper right corner of the iMedidata screen. If an eLearning is required for a study and has not yet been taken, the link to the eLearning will appear under the study name in the *Studies* pane located in the center of the iMedidata screen; once the successful completion of the eLearning has been recorded, access to the study in Rave will be granted, and a *Rave EDC* link will replace the eLearning link under the study name.

Site staff that have not previously activated their iMedidata/Rave account at the time of initial site registration approval for the study in RSS will receive a separate invitation from iMedidata to activate their account. Account activation instructions are located on the CTSU website in the Data Management section under the Rave resource materials (Medidata Account Activation and Study Invitation Acceptance). Additional information on iMedidata/Rave is available on the CTSU members' website in the Data Management > Rave section at [www.ctsu.org/RAVE/](http://www.ctsu.org/RAVE/) or by contacting the CTSU Help Desk at [name] or by e-mail at [[contact]](mailto:[contact]).

### 12.2.1 Method

This study will be monitored by the Clinical Trials Monitoring Service (CTMS). Data will be submitted to CTMS at least once every two weeks via Medidata Rave (or other modality if approved by CTEP). Information on CTMS reporting is available at <http://www.theradex.com/clinicalTechnologies/?National-Cancer-Institute-NCI-11>. On-site audits will be conducted three times annually (one annual site visit and two data audits). For CTMS monitored studies, after users have activated their accounts, please contact the Theradex Help Desk at [contact] or by email at [[contact]](mailto:[contact]) for additional support with Rave and completion of CRFs.

### 12.2.2 Responsibility for Data Submission

For ETCTN trials, it is the responsibility of the PI(s) at the site to ensure that all investigators at the ETCTN Sites understand the procedures for data submission for each ETCTN protocol and that protocol specified data are submitted accurately and in a timely

NCI Protocol #: 9892

Version Date: January 12, 2023

manner to the CTMS via the electronic data capture system, Medidata Rave.

Data are to be submitted via Medidata Rave to CTMS on a real-time basis, but no less than once every 2 weeks. The timeliness of data submissions and timeliness in resolving data queries will be tracked by CTMS. Metrics for timeliness will be followed and assessed on a quarterly basis. For the purpose of Institutional Performance Monitoring, data will be considered delinquent if it is greater than 4 weeks past due.

Data from Medidata Rave and CTEP-AERS is reviewed by the CTMS on an ongoing basis as data is received. Queries will be issued by CTMS directly within Rave. The queries will appear on the Task Summary Tab within Rave for the CRA at the ETCTN to resolve. Monthly web-based reports are posted for review by the Drug Monitors in the IDB, CTEP. Onsite audits will be conducted by the CTMS to ensure compliance with regulatory requirements, GCP, and NCI policies and procedures with the overarching goal of ensuring the integrity of data generated from NCI-sponsored clinical trials, as described in the ETCTN Program Guidelines, which may be found on the CTEP ([http://ctep.cancer.gov/protocolDevelopment/electronic\\_applications/adverse\\_events.htm](http://ctep.cancer.gov/protocolDevelopment/electronic_applications/adverse_events.htm)) and CTSU websites.

CTMS will utilize a core set of eCRFs that are Cancer Data Standards Registry and Repository (caDSR) compliant (<http://cbiit.nci.nih.gov/ncip/biomedical-informatics-resources/interoperability-and-semantics/metadata-and-models>). Customized eCRFs will be included when appropriate to meet unique study requirements. The PI is encouraged to review the eCRFs, working closely with CTMS to ensure prospectively that all required items are appropriately captured in the eCRFs prior to study activation. CTMS will prepare the eCRFs with built-in edit checks to the extent possible to promote data integrity.

CDUS data submissions for ETCTN trials activated after March 1, 2014, will be carried out by the CTMS contractor, Theradex. CDUS submissions are performed by Theradex on a monthly basis. The trial's lead institution is responsible for timely submission to CTMS via Rave, as above.

Further information on data submission procedures can be found in the ETCTN Program Guidelines ([http://ctep.cancer.gov/protocolDevelopment/electronic\\_applications/adverse\\_events.htm](http://ctep.cancer.gov/protocolDevelopment/electronic_applications/adverse_events.htm)).

### **12.3 CTEP Multicenter Guidelines**

N/A

### **12.4 Collaborative Agreements Language**

The agent(s) supplied by CTEP, DCTD, NCI used in this protocol is/are provided to the NCI under a Collaborative Agreement (CRADA, CTA, CSA) between the Pharmaceutical Company(ies) (hereinafter referred to as "Collaborator(s)") and the NCI Division of Cancer Treatment and Diagnosis. Therefore, the following obligations/guidelines, in addition to the provisions in the "Intellectual Property Option to Collaborator" ([http://ctep.cancer.gov/industryCollaborations2/intellectual\\_property.htm](http://ctep.cancer.gov/industryCollaborations2/intellectual_property.htm)) contained within the

terms of award, apply to the use of the Agent(s) in this study:

1. Agent(s) may not be used for any purpose outside the scope of this protocol, nor can Agent(s) be transferred or licensed to any party not participating in the clinical study. Collaborator(s) data for Agent(s) are confidential and proprietary to Collaborator(s) and shall be maintained as such by the investigators. The protocol documents for studies utilizing Agents contain confidential information and should not be shared or distributed without the permission of the NCI. If a copy of this protocol is requested by a patient or patient's family member participating on the study, the individual should sign a confidentiality agreement. A suitable model agreement can be downloaded from: <http://ctep.cancer.gov>.
2. For a clinical protocol where there is an investigational Agent used in combination with (an)other Agent(s), each the subject of different Collaborative Agreements, the access to and use of data by each Collaborator shall be as follows (data pertaining to such combination use shall hereinafter be referred to as "Multi-Party Data"):
  - a. NCI will provide all Collaborators with prior written notice regarding the existence and nature of any agreements governing their collaboration with NCI, the design of the proposed combination protocol, and the existence of any obligations that would tend to restrict NCI's participation in the proposed combination protocol.
  - b. Each Collaborator shall agree to permit use of the Multi-Party Data from the clinical trial by any other Collaborator solely to the extent necessary to allow said other Collaborator to develop, obtain regulatory approval or commercialize its own Agent.
  - c. Any Collaborator having the right to use the Multi-Party Data from these trials must agree in writing prior to the commencement of the trials that it will use the Multi-Party Data solely for development, regulatory approval, and commercialization of its own Agent.
3. Clinical Trial Data and Results and Raw Data developed under a Collaborative Agreement will be made available to Collaborator(s), the NCI, and the FDA, as appropriate and unless additional disclosure is required by law or court order as described in the IP Option to Collaborator ([http://ctep.cancer.gov/industryCollaborations2/intellectual\\_property.htm](http://ctep.cancer.gov/industryCollaborations2/intellectual_property.htm)). Additionally, all Clinical Data and Results and Raw Data will be collected, used and disclosed consistent with all applicable federal statutes and regulations for the protection of human subjects, including, if applicable, the *Standards for Privacy of Individually Identifiable Health Information* set forth in 45 C.F.R. Part 164.
4. When a Collaborator wishes to initiate a data request, the request should first be sent to the NCI, who will then notify the appropriate investigators (Group Chair for Cooperative Group studies, or PI for other studies) of Collaborator's wish to contact them.
5. Any data provided to Collaborator(s) for Phase 3 studies must be in accordance with the guidelines and policies of the responsible Data Monitoring Committee (DMC), if there is a DMC for this clinical trial.

6. Any manuscripts reporting the results of this clinical trial must be provided to CTEP by the Group office for Cooperative Group studies or by the principal investigator for non-Cooperative Group studies for immediate delivery to Collaborator(s) for advisory review and comment prior to submission for publication. Collaborator(s) will have 30 days from the date of receipt for review. Collaborator shall have the right to request that publication be delayed for up to an additional 30 days in order to ensure that Collaborator's confidential and proprietary data, in addition to Collaborator(s)'s intellectual property rights, are protected. Copies of abstracts must be provided to CTEP for forwarding to Collaborator(s) for courtesy review as soon as possible and preferably at least three (3) days prior to submission, but in any case, prior to presentation at the meeting or publication in the proceedings. Press releases and other media presentations must also be forwarded to CTEP prior to release. Copies of any manuscript, abstract and/or press release/ media presentation should be sent to:

Email: [[contact]](mailto:[contact])

The Regulatory Affairs Branch will then distribute them to Collaborator(s). No publication, manuscript or other form of public disclosure shall contain any of Collaborator's confidential/ proprietary information.

## 13. STATISTICAL CONSIDERATIONS

### 13.1 Study Design/Endpoints

The **primary safety endpoint** of this study is DLT, and the first primary objective is the determination of the MTD and recommended phase II dose for oral triapine when used concomitantly with cisplatin chemoradiation.

The **primary PK endpoint** of this study is oral bioavailability of triapine, which will be determined with sufficient precision that the 95% CI of the mean population bioavailability falls within 80-125% of that mean. Based on reported preliminary data and assuming a normal distribution at log base 10 level, a true bioavailability rate of 0.67, and a standard deviation of 0.175 at log base 10 level, with 28 patients on RP2D, we will be able to establish the bioavailability with the 95% confidence interval of the population mean falling within 0.53-0.83.

Other PK parameter, including AUC, Cmax, Tmax and T1/2 will be evaluated in the expansion cohort. Descriptive statistics will be used.

The **secondary efficacy endpoints** include metabolic complete response (mCR) by FDG-PET/CT, clinical overall response (OR), overall survival (OS) and progression free survival (PFS).

For the first dose level, 3 patients were enrolled without issues. Given the scarcity of patients and the thus far favorable toxicity profile, dose level 2 will be enrolled per an accelerated titration approach using a single patient cohort. Dose escalation will revert to the standard 3+3 design if the

patient on dose level 2 experiences a DLT or a  $\geq$  grade 2 toxicity or when dose level 3 is reached. The standard 3+3 design is as follows: Escalation at 0/3 DLTs, dose-reduction if  $>1/3$  DLT, and expansion to 6 if 1/3 DLTs. DLT is defined as the severe toxicity event that leads to the termination of the treatment as defined in section 5.5. The highest dose level where  $<2/6$  DLTs are observed will be declared MTD.

13.1.1 The RP2D will be determined as described in section 5.1.2. Once the RP2D is determined, two expansion cohorts will be enrolled. Subjects will be enrolled into a non-HIV+ cohort (n=12) to further expand pharmacokinetic investigations and provide additional safety information. Additionally, up to 28 HIV+ cervical cancer patients (including the patients who were treated at the RP2D during the dose escalation stage) will be treated on RP2D to determine whether active HIV antiretroviral therapy impacts the antitumor activity of triapine. A Bayesian continuous monitoring will be used to ensure that the true DLT rate is controlled at 20%. To establish the stopping rule, a week prior distribution of DLT rate is set to be beta ( $\alpha=1, \beta=5$ ). If the posterior probability that the true underlying DLT rate exceeds 20% at RP2D is 70% or higher then the study accrual will be suspended and the toxicity data will be examined by the PI and the research team, who will subsequently decide on whether the trial should be terminated or not.

The enrollment suspension rule using the Bayesian analysis mentioned above can be represented as a table of possible outcomes for DLTs, as shown below.

Bayesian rule for suspending enrollment	
Suspend accrual if n patients experience a DLT	in N patients treated
2	3-4
3	5-8
4	9-13
5	14-17
6	18-22
7	23-26
8	27

The operating characteristics of this study design can be expressed in terms of probability of early suspending the enrollment at RD2P under the assumptions of various the true rates of DLT. The following table calculated these probabilities for a single dose level based on the simulation of 10,000 hypothetical trials.

Frequentist properties of Bayesian rule for suspending enrollment		
Probability of DLT	Probability of suspending	Median sample size for

	the enrollment	each dose level
0.1	0.10	28
0.17	0.32	28
0.2	0.45	28
0.25	0.66	13
0.3	0.83	8

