### 5.1.3 Dose to be used for expansion

Dose escalation has been completed as of Amendment 10. The dose to be used for expansion is 100 mg triapine PO daily in combination with cisplatin based chemoradiation as described in this protocol. Data supporting this dose decision are detailed below and have been discussed with the CTEP Medical Monitor.

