### 5.1.3.3 Pharmacokinetics

Summary PK of triapine in the dose escalation is reported below. PK is comparable to earlier reports of triapine for both routes. PO bioavailability observed in this trial was 66%, which is also comparable to previous reports of 67% (Chao 2012). There was no discernable difference between triapine exposure at 100 vs 150 mg PO, and between patient variability at each dose level was substantial.

Pharmacokinetics of triapine at 50 mg IV (left), 100 mg PO (middle) or 150 mg PO (right).

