#### Bioavailability of triapine.

[figure not shown]
PO_DOSE		F
100	Geometric Mean	0.75
	Geometric SD	2.2
	N	6
150	Geometric Mean	0.54
	Geometric SD	1.5
	N	4
Overall	Geometric Mean	0.66
	Geometric SD	1.9
	N	10

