### 13.3 Data Analysis

#### 13.3.1 Analysis Sets

Evaluable patients: patients who meet all of the protocol inclusion/exclusion criteria and begin treatment with the protocol regimen.

Evaluable patients for DLT: evaluable patients who received at least 80% of the treatment intended during the DLT follow up period as defined in section 5.5 and patients who received any amount of treatment and experienced a protocol defined DLT which leads to the termination of the treatment are evaluable for DLT.

Safety set: data from all evaluable patients who receive initial treatment of the study treatment will be used in the analysis of safety.

Efficacy set: data from all evaluable patients who receive initial treatment of the study treatment will be used in the analysis of efficacy endpoints.

PK and correlative biomarker set: the data from all study-eligible patients (i.e. those meeting all of the protocol inclusion/exclusion criteria) who begin the study treatment and have adequate blood and tissue samples taken will be used in the analyses to address the PK and correlative biomarker aims.

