### 13.3.5 Analysis of PK Data

The oral bioavailability of triapine will be determined with sufficient precision that the 95% CI of the mean population bioavailability falls within 80-125% of that mean. Based on reported preliminary data and assuming a normal distribution at log base 10 level, a true bioavailability rate of 0.67, and a standard deviation of 0.175 at log base 10 level, with 28 patients on RP2D, we will be able to establish the bioavailability with the 95% confidence interval of the population mean falling within 0.53-0.83.

Standard PK parameters will be determined and will include Cmax, Tmax, Cl, Vss, and half-life. These parameters will be descriptively reported.

The association of methemoglobin proportion (%) and PK parameters will be evaluated by Spearman correlation coefficients.

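### The precision promised for the primary PK endpoint from 28 patients rests on an outdated SD; at the trial's own bioavailability variability the 80-125% target will probably be missed

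*Combined protocol and SAP*

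**What the plan says.** Oral bioavailability (F) is a primary objective (section 1.1.2) and the primary PK endpoint (section 13.1). The precision target is that "the 95% CI of the mean population bioavailability falls within 80-125% of that mean". Sections 13.1 and 13.3.5 both assume a log-normal F, a true value of 0.67 and "a standard deviation of 0.175 at log base 10 level, with 28 patients on RP2D", and conclude that the trial will deliver "the 95% confidence interval of the population mean falling within 0.53-0.83". The source given for the assumptions is preliminary data.

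Section 5.1.3 reports that escalation is finished and states: "The dose to be used for expansion is 100 mg triapine PO daily". The table headed "Bioavailability of triapine" under section 5.1.3.3 gives the trial's own F:

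| Oral dose | n | Geometric mean | Geometric SD |
|---|---|---|---|
| 100 mg | 6 | 0.75 | 2.2 |
| 150 mg | 4 | 0.54 | 1.5 |
| Overall | 10 | 0.66 | 1.9 |

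The accompanying text, speaking of exposure, says that "between patient variability at each dose level was substantial".

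On patient numbers, section 13.1.1 adds a "non-HIV+ cohort (n=12) to further expand pharmacokinetic investigations" to a cohort of up to 28 HIV+ patients, and counts patients treated at the RP2D during escalation within the 28. Section 13.2.1 speaks of up to 28 additional HIV+ patients. The PK set in 13.3.1 takes all eligible patients who start treatment and "have adequate blood and tissue samples taken will be used in the analyses to address the PK and correlative biomarker aims", with no limit at 28.

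**The concern.** The escalation results were written into section 5, but the SD in section 13 was left as it was. The observed mean (0.66) supports the assumed 0.67; the observed spread does not support 0.175. CI width is proportional to the SD, so a precision statement for a primary endpoint now conflicts with data in the same document. Because sections 13.1 and 13.3.5 do not say which 28 patients are meant, a reader also cannot tell whether 28, 40 or 46 patients will be analysed, and that choice affects whether the target is met.

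**Working it through.** **Method.** On the log10 scale the CI half-width is t(0.975, n−1) × SD / √n. The target of 80-125% means a half-width of at most log10(1.25) = 0.0969.

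**The plan's own figure.** With SD 0.175, n = 28 and t = 2.052, the half-width is 2.052 × 0.175 / √28 = 0.0679. The CI is 85.5-116.9% of the mean, or 0.573-0.783 around 0.67. The target band is 0.80 × 0.67 = 0.536 to 1.25 × 0.67 = 0.8375, stated as 0.53-0.83. The claim follows, and 16 patients would have been enough.

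**Observed SDs** (log10 of the geometric SD):
- 100 mg: log10(2.2) = 0.342, 5 df
- 150 mg: log10(1.5) = 0.176, 3 df
- Overall: log10(1.9) = 0.279, 9 df
- Pooled within dose: √[(5 × 0.3424² + 3 × 0.1761²) / 8] = 0.291, 8 df

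As a check on reading the table, recombining the two dose rows gives geometric mean 0.66 and geometric SD 1.93, against 0.66 and 1.9 reported. The 100 mg, overall and pooled figures share patients and are not independent.

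**Could this be chance around 0.175?** The chi-square 95% intervals for the log10 SD are 0.214-0.840 (100 mg), 0.197-0.558 (pooled) and 0.192-0.509 (overall). All exclude 0.175. Allowing for rounding of the reported geometric SDs, the lower limits are still at least 0.208, 0.190 and 0.184.

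**Consequence at n = 28.** The target is met only if the sample SD is at most 0.0969 × √28 / 2.052 = 0.250. With the SD taken as known, the chance of that is P[χ²(27) ≤ 27 × 0.250² / SD²]. Allowing for uncertainty in the observed SD, it is P[F(27, df) ≤ 0.250² / SD²].

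| log10 SD | Expected CI, % of mean | Chance, SD known | Chance, SD uncertain | n for expected CI to fit |
|---|---|---|---|---|
| 0.175 (plan) | 85.5-116.9 | 99.9% | – | 16 |
| 0.279 (overall) | 78.0-128.3 | 25% | 31% | 35 |
| 0.291 (pooled) | 77.1-129.7 | 16% | 26% | 38 |
| 0.342 (100 mg) | 73.7-135.8 | 2% | 13% | 51 |

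**If more RP2D patients are analysed.** If both cohorts fill, 28 + 12 = 40. If none of the six escalation patients at 100 mg counts toward the HIV+ 28, the total is 40 + 6 = 46. The largest sample SD that meets the target is then 0.303 or 0.326.

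| n | log10 SD | Expected CI, % of mean | Chance, SD known | Chance, SD uncertain |
|---|---|---|---|---|
| 40 | 0.279 | 81.4-122.8 | 80% | 58% |
| 40 | 0.291 | 80.7-123.9 | 66% | 51% |
| 40 | 0.342 | 77.7-128.7 | 17% | 29% |
| 46 | 0.279 | 82.6-121.0 | 95% | 68% |
| 46 | 0.291 | 81.9-122.0 | 88% | 61% |
| 46 | 0.342 | 79.1-126.4 | 35% | 37% |

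**The case against.** The statement is explicitly conditional on its SD and is correct on that condition, so this is an unrevised assumption and not a miscalculation. That is accepted.

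The contrary evidence is also small. The sharpest figures rest on six patients, individual values are not shown, and chi-square intervals for an SD lean on log-normality, so one outlier could drive the 2.2. The 150 mg SD agrees with the plan, and the two dose variances do not differ significantly (ratio 3.8 on 5 and 3 df, two-sided p about 0.30). This is why the conclusion is only that a miss is likely. Pooling within dose gives the 150 mg patients their due weight, and the interval still excludes 0.175.

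The preliminary data could be combined with the new data instead of replaced. Their degrees of freedom are not given. If they were 9 or 19 (an assumption), combining with the pooled 0.291 gives 0.237 or 0.216, below the 0.250 needed at n=28; with 5 df it gives 0.253, just above. But section 2.4.1 says the earlier studies used a different oral formulation, which weakens the case for combining.

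Finally, the final CI will be reported at its true width, and at the overall SD the miss is narrow (78-128%). This limits the severity but does not make the present wording right. Two caveats on the larger N also stand. Analysing HIV+ and non-HIV+ patients together assumes that one mean and one SD serve both. And the calculations at 46 treat the six escalation patients as new data, which shifts the result by only about 1 percentage point.

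**Conclusion.** The concern holds. The calculation is sound on its own inputs, but its SD is not supported by the trial's own data in the same version. At n=28 the expected CI is between 78-128% and 74-136% of the mean, and the chance of meeting 80-125% is 2-25% with the SD taken as known, or 13-31% allowing for its uncertainty. Success remains possible, because the intervals for the observed SDs include values below 0.250. With 40 or 46 patients the expected CI meets the target at the overall and pooled SDs but not at the 100 mg SD. These figures assume log-normal F and an expansion-cohort spread like that seen in escalation. The harm is an over-optimistic precision statement and an undefined N for a primary endpoint. The estimate is not biased, and no dose decision, test or stopping rule is affected. It should be fixed.

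**What to change.** In sections 13.1 and 13.3.5:

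1. Replace the log10 SD of 0.175 with the observed range, about 0.28-0.34, citing the bioavailability table in 5.1.3.3.
2. Name one PK analysis N in advance: all patients at the RP2D with paired Day 1 IV and Day 8 oral profiles. This is a subset of the PK set in 13.3.1 and matches the RP2D wording of 13.1. It is about 40 if both cohorts fill, and at most 46.
3. Restate the expected CI around 0.67. At n=40 it is 0.55-0.82 (SD 0.279, target met) or 0.52-0.86 (SD 0.342, missed). At n=46 it is 0.55-0.81 or 0.53-0.85 (79-126% of the mean, narrowly missed).
4. Say that 80-125% may not be reached: allowing for uncertainty in the SD, the chance is 29-58% at n=40 and 37-68% at n=46. Keep 0.53-0.83 only as the target band.

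The cost is wording in two sections and a less favourable stated precision. No patients or samples are added, since the study calendar already schedules PK sampling in Weeks 1 and 2.
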